In this extension trial, subjects enrolling from the double-blind Trial 156-13-210 will have monthly visits and transaminase level assessments for the first 18 months while the treatment code from Trial 156-10-210 remains blinded, to ensure that all subjects have adequate safety monitoring during this period of susceptibility. Once unblinding occurs, it can be determined which subjects received tolvaptan in Trial 156-13-210. These subjects may have their trial visits/hepatic transaminase monitoring change to every 3 months sooner as their previous tolvaptan exposure in Trial 156-13-210 can count towards the 18-month threshold. If subjects approaching the 18-month threshold have had prior transaminase abnormalities ($>$ 2 \times upper limit of normal [ULN]), the investigator is responsible for contacting the medical monitor to confirm the change in frequency from monthly to every 3 months. Subjects enrolling from the open-label Trial 156-08-271 will have transaminase assessments conducted every 3 months, since they will have already received tolvaptan for at least 18 months. The current IB lists all of the tolvaptan trials. Subjects enrolling in this trial who were in a previous ADPKD tolvaptan trial other than Trials 156-13-210 and 156-08-271 will have monthly visits and alanine aminotransferase (ALT) level assessments for the first 18 months.

Protocol 156-13-211

2 Trial Rationale and Objectives

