3.7.1.3 Monthly Visit (± 7 days)

The following subjects will return for a monthly visit to assess safety and tolerability of IMP and to monitor liver function.

- Subjects enrolling from the double-blind Trial 156-13-210 will have monthly trial visits/ALT level assessments for the first 18 months while treatment code from Trial 156-13-210 remains blinded, to ensure that they have adequate safety monitoring during this period of susceptibility. Once unblinding occurs, it can be determined which subjects received tolvaptan in Trial 156-13-210. These subjects may have their trial visits/hepatic transaminase monitoring change to every 3 months sooner as their previous tolvaptan exposure in Trial 156-13-210

Protocol 156-13-211

can count towards the 18-month threshold. The investigator will need to discuss the change in frequency with the medical monitor before instituting the change.

- Subjects from prior tolvaptan trials other than Trial 156-08-271 will have monthly trial visits/ALT level assessments for the first 18 months. After that, the trial visits/ALT monitoring will be conducted every 3 months after the change in frequency is confirmed with the medical monitor.
- Subjects enrolling from the open-label Trial 156-08-271 who have greater than 18 months of exposure to tolvaptan will have trial visits/ALT monitoring conducted every 3 months.

The following will be assessments will be completed:

1. Review dietary recommendations and compliance.

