3.4 Trial Visit Window

Due to the extended duration of the study, the individual patient data will be summarized by period.

For assessments recorded at clinic visits, except for the hepatic monitoring for the subjects from Trial 156-08-271, data will be derived by mapping the study day of the assessment into corresponding time windows as specified in [Table 3.4.1](#). Study day is calculated as: date of assessment - date of enrollment (ie, screening or baseline date) + 1. If there are multiple observations within the same study time window, only the last observation within that study week will be used for the summary tables. The time window mapping rules are applicable to all post first dose safety and efficacy assessments (unless otherwise stated) that are assessed at the scheduled or unscheduled visits (excluding early termination visits/end of treatment visits).

Table 3.4.1 Mapping of clinic visit assessments to study month (except for hepatic monitoring for Subjects from Trial 156-08-271)

Study Month	Study Day Interval
Monthly Visit	
Month 1	2 – 46
Month 2	47 – 76
Month 3	77 – 107
Month 4	108 – 137
Month 5	138 – 168
Month 6	169 – 198
Month 7	199 – 229
Month 8	230 – 259
Month 9	260 – 290
Month 10	291 – 320
Month 11	321 – 351
Month 11	352 – 381
Month 13	382 – 412
Month 14	413 – 442

Protocol 156-13-211

Month 15	443 – 473
Month 16	474 – 503
Month 17	504 – 534
Month 18	535 – 595
Every 3 Months	
Month 21	596 – 686
Month 24	687 – 778
Month 27	779 – 869
Month 30	870 – 961
Month 33	962 – 1052
Month 36	1053 – 1144
Month 39	1145 – 1235
Month 42	1236 – 1327
Month 45	1328 – 1418
Month 48	1419 – 1510
Month 51	1511 – 1601
...	...

Note: Early Termination/End of Treatment (\pm 7 days)

Once Trial 156-13-210 unblinding occurs, it can be determined which subjects received tolvaptan in Trial 156-13-210. These subjects may have their trial visits/hepatic transaminase monitoring changed to every 3 months sooner as their previous tolvaptan exposure in Trial 156-13-210 can count towards the 18-month threshold.

For assessments for hepatic monitoring recorded at clinic visits, for the subjects from Trial 156-08-271, data will be derived by mapping the study day of the assessment into corresponding time windows as specified in [Table 3.4.2](#).

Study Month	Study Day Interval
Every 3 Months (\pm 45 days)	
Month 3	2 – 137
Month 6	138 – 229
Month 9	230 – 320
Month 12	321 – 412
Month 15	413 – 503
Month 18	504 – 595
Month 21	596 – 686
Month 24	687 – 778
Month 27	779 – 869

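### SAP 3.4 maps subjects on 3-monthly visits to monthly windows that accept unscheduled visits, so their in-between months hold only unscheduled values and by-month means can be selectively observed

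*SAP*

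**What the plan says.** The mapping rule is in SAP 3.4. Its scope is wide: "For assessments recorded at clinic visits, except for the hepatic monitoring for the subjects from Trial 156-08-271, data will be derived by mapping". The target is Table 3.4.1, which is monthly to Month 18 and 3-monthly afterwards. The rule covers post-first-dose assessments "that are assessed at the scheduled or unscheduled visits", leaving out early termination and end-of-treatment visits. If a window holds several values, "only the last observation within that study week will be used for the summary tables". I read study week there as the time window, the term used earlier in the same sentence.

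Table 3.4.2 gives 3-month windows, but only for hepatic monitoring of 271 subjects. Two sets of 3-monthly data therefore stay on the monthly table:

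- **210 tolvaptan subjects after an early switch, all data.** SAP 3.4 says "These subjects may have their trial visits/hepatic transaminase monitoring changed to every 3 months sooner" and gives them no other windows.
- **271 subjects, non-hepatic data.** Protocol 3.7.1.3 sets a 3-month interval for this group: "Subjects enrolling from the open-label Trial 156-08-271 who have greater than 18 months of exposure to tolvaptan will have trial visits/ALT monitoring". The visit itself is 3-monthly, so sodium, creatinine, urinalysis and vital signs are too.

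SAP 5.2 summarizes observed values only. SAP 8.3 and 8.4 summarize vital signs and sodium by parent study and prior treatment, so the 271 subjects form a group of their own.

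**The concern.** A by-month mean can be compared with its neighbours only if roughly the same subjects contribute to each month for the same reason. For subjects on 3-monthly visits, the quarter months hold almost everyone, and the in-between months hold only those who came in outside the schedule. For liver tests the protocol makes such visits depend on the result: under Protocol 3.7.2.4.1, a transaminase or bilirubin value above 2 x ULN calls for a retest within 72 hours, then at least weekly tests for a month while values stay abnormal. With no imputation, subjects who did not come in drop out of the summary.

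Long-term safety is the trial's only objective, and changes from baseline are a planned output (SAP 8). A rise in an in-between month could be read as a drug or cohort signal when it reflects who was measured. Printing the denominator shows that few subjects contributed. It does not show that they were selected.

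**Working it through.** The plan states no figure for this point and has no power calculation, so the check is on the windows.

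**1. Do the windows follow a simple rule?** Boundaries at 30.4375 x (m ± 0.5) + 1 days reproduce the printed limits for Months 2-17 to within 1 day. For Month 6, 168.4 and 198.8 give days 169-198, as printed.

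**2. Where do 3-monthly visits fall?** With baseline as Day 1, the nominal day is 30.4375 x m, rounded, plus 1. The allowed range is ± 14 days (Protocol 3.7.1.4).

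| Month | Nominal day | Allowed days | Table 3.4.1 window | Table 3.4.2 window |
|---|---|---|---|---|
| 3 | 92 | 78-106 | 77-107 | 2-137 |
| 6 | 184 | 170-198 | 169-198 | 138-229 |
| 9 | 275 | 261-289 | 260-290 | 230-320 |
| 12 | 366 | 352-380 | 352-381 | 321-412 |
| 15 | 458 | 444-472 | 443-473 | 413-503 |
| 18 | 549 | 535-563 | 535-595 | 504-595 |

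(Table 3.4.1 labels the 352-381 row Month 11 a second time; I treat it as Month 12.) Every allowed visit day falls in its own quarter-month window, so no scheduled visit reaches an in-between month.

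**3. How many windows are left without a scheduled value?**

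- 271 subjects: 18 windows less Months 3, 6, 9, 12, 15 and 18 = 12.
- A 210 subject switching at Month 6: Months 7-18 are 12 windows, less 9, 12, 15 and 18 = 8. Month 6 is illustrative: 18 months less about 12 months in Trial 210. No unblinding date is given.

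**4. Where do liver retests go?** Take an abnormal result on day 184 and tests 3, 7, 14, 21 and 28 days later. Days 187, 191 and 198 stay in Month 6, and under the last-value rule they replace the scheduled value. Days 205 and 212 fall in Month 7. A monthly test on day 242 falls in Month 8.

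**5. How much of an in-between month is unscheduled?** Let q be the share of the group on 3-monthly visits, u the share of those with an unscheduled value in the window, and a the attendance of monthly subjects. The unscheduled share is qu / (qu + (1 - q)a). None of the three is in the documents; I assume a = 0.9.

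- u = 5%: 5% at q = 0.50, 14% at 0.75, 33% at 0.90, 51% at 0.95, 100% at q = 1.
- The share passes one half when q > 0.9 / (0.9 + u): 0.978 for u = 2%, 0.947 for u = 5%, 0.90 for u = 10%.

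**6. What could that do to a mean?** Assume mean ALT of 0.55 x ULN at routine visits and 2.5 x ULN at retests, with u = 5%. Observed against full-cohort mean: 0.65 against 0.60 at q = 0.50; 0.83 against 0.62 at q = 0.75; 1.20 against 0.64 at q = 0.90. These figures show direction and shape and are not estimates for this trial.

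**7. Does the study-day anchor matter?** SAP 3.4 counts from screening or baseline, and screening may be up to 30 days earlier. With a 14-day lead, 52-55% of allowed days at Months 3-15 stay in their own monthly window; with a 30-day lead, none do. The counts in step 3 therefore need the baseline anchor. Table 3.4.2 is robust to this: Month 6 with a 30-day lead is day 214, allowed days 200-228, still inside 138-229.

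**The case against.** A reader might infer that the in-between months are filled mainly by problem-driven retests and will look worse than the quarter months. The documents do not support that.

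- **210 group.** The switch is optional and follows unblinding. Subjects who have not switched still supply scheduled values every month, and step 5 shows that unscheduled values form the majority only when about 90-98% have switched, under assumed rates.
- **271 group.** Its ALT values are outside Table 3.4.1. For the remaining data the visible text requires no retest after an abnormal result, and Protocol 3.7.2.3 says that extra visits are usual in some regions and are recorded as unscheduled. These values are unscheduled but not necessarily problem-driven.
- **Who stays on monthly visits.** It is tempting to say that subjects with earlier values above 2 x ULN are kept on monthly visits. Protocol 1.3 says only that "the investigator is responsible for contacting the medical monitor to confirm the change in frequency from monthly to every 3 months". That is contact, not refusal, and Protocol 3.7.1.3 asks for a discussion with the medical monitor for every 210 subject.
- **Impact.** SAP 8 plans no inference. The main liver and sodium outputs are ever-exceeded frequencies, Hy's criteria and excursions, which do not depend on the month window.
- **Possible exceptions.** SAP 3.4 allows other rules to be stated elsewhere. Most of the SAP laboratory section, between 8.1.2 and 8.3, was not in the text available to me, so a rule for by-visit laboratory tables may be there. The vital-signs section, which is legible, states none. It is also unclear whether local-laboratory retests enter these tables.

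These points limit the claim. They leave standing the mismatch between visit schedule and windows, and the replacement of scheduled values by retests.

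**Conclusion.** The mismatch is real and follows from the text of SAP 3.4. Counted from baseline, the in-between monthly windows of a subject on 3-monthly visits can hold only unscheduled values. In switched 210 subjects these are often abnormality-driven for liver tests; in 271 subjects they are non-hepatic and of mixed origin. By-month means and changes from baseline can therefore be selectively observed. The effect is strongest where a group is wholly or almost wholly on 3-monthly visits, as the 271 group is. Retests can also displace scheduled values in the quarter months.

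The extent in windows is 12 of 18 for 271 subjects, and 8 of 12 for the illustrative 210 subject. The size of any bias in a mean is unknown, because the documents give neither the number who switch nor the rate and reasons of unscheduled visits. The incidence tables stand. This is a correction that should be made to descriptive by-period summaries; it does not threaten the trial's main safety counts.

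**What to change.** Three changes to SAP 3.4:

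1. For by-visit means and changes from baseline, use the scheduled-visit value instead of the last value of any kind. This step is essential: wider windows alone would still let a retest on day 205 or 212 replace a scheduled day-184 value in the Month 6 window of Table 3.4.2.
2. Map all assessments of subjects on a 3-monthly schedule with the windows of Table 3.4.2: 271 subjects with more than 18 months of exposure from Day 1, and 210 and other subjects from the date of their switch.
3. Keep unscheduled values for worst-value, incidence and time-to-onset tables, so that no safety signal is lost.

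The cost is some SAP wording and programming, and slightly different windows across cohorts. Quarterly tables for every cohort are not needed and would give up monthly detail for subjects who do attend monthly. If the laboratory section already restricts by-visit tables to scheduled visits, a cross-reference would cover the first change for laboratory data; vital signs would still need it.

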5.1 Data for Analysis

The following datasets are defined for this trial:

- I. Enrolled Population: all subjects who were enrolled to this open-label trial.
- II. Safety Population: all subjects in the Enrolled Sample who take at least one dose of IMP.

5.2 Handling of Missing Data

The majority of missing data are expected to be caused by patients who dropped out of the study before completion. The pattern of drop out will be summarized by disposition of patients and reasons for discontinuation.

All safety/efficacy data will be summarized for observed (non-missing) values only.

No missing data will be imputed under the assumption of missing at random.

6 Summary of Study Data

6.1 Subject Disposition

Disposition of all enrolled patients, as well as reasons for discontinuation, will be summarized by parent study and the treatment groups in the parent study (rollover from Trial 156-08-271, Trial 156-13-210 and Other Trials).

In addition, the number (percentage) of patients completing a certain number of months (in the categories of $\geq 1, 2, 3, 4, 6, 7, 8, 9, 10, 11, 12, 13, 14, 15, 16, 17, 18, 21, 24, 27$ months) will be tabulated by parent study.

6.2 Demographic and Baseline Characteristics

Demographic and baseline characteristics (including medical history) will be from either the last visit assessments from parent trials or the screening visit from this trial (the time between the last visit assessments from the previous trial and the screening visit for this trial is within 30 days). Summary statistics including mean, median, minimum, maximum, and standard deviation will be used to describe continuous variables such as age. Frequency distributions will be tabulated for categorical variables such as race. Demographic and baseline characteristics will be tabulated and presented for all patients in the Safety Analysis Set by parent study, also by the treatment group in the parent study.

Protocol 156-13-211

6.3 Baseline Disease Evaluation

A short PKD history survey will be completed during screening to capture information from the subject's recollection, and documented past medical history where available. Baseline disease evaluation will be tabulated and presented for all patients in the Safety Analysis Set by parent study, also by the treatment group in the parent study.

6.4 Treatment Compliance

Subject compliance will be monitored by pill counts as IMP is returned. Any subject who, without the instruction of the investigator, discontinues tolvaptan investigational product, discontinues tolvaptan for 30 consecutive days or misses > 30% of the doses intended for a period between visits (whichever is greater) will be deemed noncompliant. Depending on the circumstances leading to noncompliance, the subject may be withdrawn from the trial or discontinued from investigational product administration by the investigator and/or sponsor. It is preferred that subjects who discontinue tolvaptan, or are withdrawn by the investigator for reasons other than noncompliance or lost to follow-up, will continue with regularly scheduled visits completing all procedures as provided in the protocol.

Treatment compliance will be calculated by dividing the total dosage taken by the total dosage the subjects are scheduled to take during the treatment phase based on the Study Medication panel of the case report form (CRF).

6.6 Protocol Deviations

Protocol deviations occurring to patients will be listed and summarized (only for major protocol deviations) by patient type by parent trial.

7 Efficacy Analysis

No efficacy analyses are planned.

8 Safety Analyses

Safety analysis will be conducted based on the Safety Population, which is defined as all subjects in the Enrolled Population who take at least one dose of IMP. Safety variables to be analyzed include clinical laboratory tests, vital signs, and AEs. CCI [REDACTED]

In general, baseline measurements of safety variables are defined as the last measurements prior to the first dose of IMP in Trial 156-13-211. Safety variables will be summarized by descriptive statistics, (eg, proportion, mean, median, SD, minimum, and maximum values). Summary statistics, including changes from baseline, will be provided for safety variables based on all available data. No inferential statistical analyses of the safety variables will be performed.

Safety variables to be analyzed include:

- Adverse events
- Vital signs
- Clinical laboratory assessments
- Serum transaminase elevations for frequency (2x, 3x, 5x and 10x ULN), time to onset, time to peak levels, time of offset (< 3x, 2x, or 1x ULN), response to de-challenge and re-challenge and frequency of progression to Hy's laboratory criteria (ALT or AST > 3x ULN and bilirubin, total (BT), > 2x ULN without alkaline phosphatase > 2x ULN)
- Serum sodium excursions above 145, 150, or 155 mmol/L or below 136, 130, or 125 mmol/L

8.1 Adverse Events

ADPKD is a progressive disorder involving the kidney, liver and occasionally other organ systems. A number of AEs may be associated with this disorder including urine

Protocol 156-13-211

concentration defects, hypertension, renal pain, renal infection, nephrolithiasis, hematuria, and ESRD. As such, these events are considered “expected” in this trial population and will not qualify for the purposes of regulatory expedited reporting (eg, Suspected Unexpected Serious Adverse Reaction and investigational new drug [IND] safety reports).

8.1.1 Definitions

An AE is defined as any untoward medical occurrence associated with the use of an IMP in humans, whether or not considered IMP related.

A suspected adverse reaction means any AE for which there is a reasonable possibility that the IMP caused the AE. For the purpose of IND safety reporting, “reasonable possibility” means there is evidence to suggest a causal relationship between the IMP and the AE. Suspected adverse reaction implies a lesser degree of certainty about causality.

A serious adverse event (SAE) includes any event that results in any of the following outcomes:

1. Death
2. Life-threatening, ie, the subject was, in the opinion of the investigator, at immediate risk of death from the event as it occurred. It does not include an event that, had it occurred in a more severe form, might have caused death.
3. Persistent or significant incapacity or substantial disruption of the ability to conduct normal life functions.
4. Requires inpatient hospitalization or prolongs hospitalization (NOTE: A pre-scheduled hospitalization is not considered an SAE.)
5. Congenital anomaly/birth defect
6. Other medically significant events that, based upon appropriate medical judgment, may jeopardize the subject and may require medical or surgical intervention to prevent one of the outcomes listed above, eg, allergic bronchospasm requiring intensive treatment in an emergency room or home, blood dyscrasias or convulsions that do not result in hospitalization, or the development of drug dependency or drug abuse.

Nonserious AEs are all AEs that do not meet the criteria for a "serious" AE.

Immediately Reportable Event (IRE):

- Any SAE
- Any AE (whether serious or nonserious) that necessitates discontinuation of IMP.
- Any subject with a new liver test abnormality meeting the AE (whether serious or nonserious) or laboratory threshold criteria (whether considered an AE or not) for hepatic eCRF reporting.
- Any subject reporting an AE of special interest (eg, skin neoplasms or glaucoma).
- Pregnancies are also defined as IREs. Although normal pregnancy is not an AE, it will mandate IMP discontinuation and must be reported on an IRE form to Otsuka

Protocol 156-13-211

Pharmaceutical Development & Commercialization, Inc. (OPDC). Pregnancy will only be documented on the AE eCRF if there is an abnormality or complication.

- Additionally, in the EU region, events involving overdose, misuse and abuse as well as reported lack of efficacy must also be reported as IREs.

All AEs will be coded by system organ class (SOC) and Medical Dictionary for Regulatory Activities (MedDRA) preferred term. The incidence of the following events will be summarized:

- a) TEAEs by severity
- b) TEAEs potentially causally related to tolvaptan
- c) TEAEs with an outcome of death
- d) Serious TEAEs
- e) Discontinuations due to TEAEs

Additionally, if the laboratory value is determined by the investigator to be an abnormal change from baseline for that subject, this is considered an AE.

Severity: Adverse events will be graded on a 3-point scale and reported as indicated on the CRF. The intensity of an adverse experience is defined as follows:

1. **Mild:** Discomfort noticed, but no disruption to daily activity.
2. **Moderate:** Discomfort sufficient to reduce or affect normal daily activity.
3. **Severe:** Inability to work or perform normal daily activity.

IMP Causality: Assessment of causal relationship of an AE to the use of the IMP:

Related: There is a reasonable probability or possibility of a temporal and causal relationship between the IMP and the AE.

Not Related: There is no temporal or causal relationship to the IMP administration.

